7.8 Unscheduled Visits

If an unscheduled visit is necessary, the following assessments should be included in the visit along with any assessments that are the reason for the visit (e.g., blood draw for a repeat of abnormal lab values):

- Measure vital signs.
- Collect concomitant medication and procedure/therapy information.
- Review and record AEs.

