6.1.3 Visit Windowing

Efficacy data will be summarized based on nominal visit indications with the exception of data captured at early termination and unscheduled visits. Efficacy data from early termination and unscheduled visits will be summarized based on mapped visit values. The analysis windows for early termination and unscheduled visits are presented in the following table.

Analysis Windows for Efficacy Assessments

Scheduled Visit	Target Study Day	Window (Days)
Week 2	15	9 to 22
Week 4	29	23 to 36
Week 6	43	37 to 50
Week 8	57	51 to 64
Week 10	71	65 to 78
Week 12	85	79 to 92
Week 14	99	93 to 106
Week 16	113	107 to 127
Week 20	141	128 to 158
Week 24	169	159 to 197
Week 32	225	198 to 239

Efficacy data collected prior to study day 9 for early termination and unscheduled visits will not be analyzed, with the exception of those identified as baseline values. Efficacy data collected at early termination and unscheduled visits after study day 239 will not be included in analyses.

The definition for the study day included in each study window is defined below:

Study Day prior to Day 1 = Visit Date – Day 1 Date

Study Day on or after Day 1 = Visit Date – Day 1 Date + 1

If an assessment's mapped visit is a visit at which the subject has data from a scheduled visit present, or if no analyses are planned for the assessment at the mapped visit, the data collected at the early termination or unscheduled visit will not be included in analyses.

In the event of multiple values from unscheduled or early termination assessments within an analysis window, the value closest to the scheduled visit target study day will be used for analyses. If two values tie as closest to the time point (for example, one value is before and the other value is after the time point), then the later value will be selected.

Safety data will be summarized based on nominal visit indications. Data captured at early termination will be assigned an Analysis Window visit based on the "Analysis Windows for Efficacy Assessments" above. Unscheduled visits will not be summarized.

Data collected at all visits will be included in the data listings with visit presented as reported by the site, except for subject reported electronic diary data. Subject reported electronic diary data listings will be presented with analysis visit, since there is no site reported visit.

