6.15.5 Clinical Laboratory Evaluation

Hematology, chemistry, urinalysis, and serology laboratory test results will be summarized with descriptive statistics at Baseline, Weeks 4, 8, 12, 16, and 24. Additionally for hematology, chemistry, and numeric urinalysis shifts from Baseline to Weeks 4, 8, 12, 16, and 24 in laboratory test results based on normal ranges will be summarized with frequency counts and percentages. Individual laboratory test results will be presented in a by-subject listing.

Laboratory values will be assigned a Severity Grade based on the Rheumatology Common Toxicity Criteria v2.0 [5]. Laboratory values with Severity Grade of 3 or 4 will be summarized at Baseline, Weeks 4, 8, 12, 16, and 24 with frequency counts and percentages. The Severity Grade of 3 or 4 will be included in by-subject listing.

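### Grade 3–4 laboratory values seen only at unscheduled draws, or at some early-termination visits, enter no laboratory table by arm, and no worst-grade table is planned

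*SAP*

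**What the plan says.** SAP 6.1.3 summarizes safety data by nominal visit and treats the two kinds of off-schedule visit differently.

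- For unscheduled visits the rule is "Unscheduled visits will not be summarized".
- For early termination it is "Data captured at early termination will be assigned an Analysis Window visit", using the windows defined for efficacy.

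SAP 6.15.5 fixes where laboratory data appear. For descriptive statistics, "laboratory test results will be summarized with descriptive statistics at Baseline, Weeks 4, 8, 12, 16, and 24". Shift tables use the same post-baseline weeks. For severe values, "Laboratory values with Severity Grade of 3 or 4 will be summarized at Baseline, Weeks 4, 8, 12, 16, and 24". Grade 3–4 values also go into a by-subject listing, and SAP 6.1.3 has listings cover all visits. Neither section plans a count of patients by worst grade or by any post-baseline occurrence.

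On the source of these data, Protocol 7.8 says an unscheduled visit includes its core checks "along with any assessments that are the reason for the visit (e.g., blood draw for a repeat of abnormal lab values"). Protocol 9.1.4 sends laboratory tests from unscheduled visits to the central laboratory, whose data are transferred to the clinical database. Protocol Appendix 1 schedules hematology, chemistry and urinalysis at early termination, and Protocol 10.2 asks for that visit as soon as possible.

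**The concern.** Severe laboratory abnormality by dose is a natural safety result for a four-arm dose-ranging trial whose objectives include safety. The usual question is how many patients in each arm ever reached Grade 3 or 4 on a given parameter. The planned tables do not answer it. They leave out draws that may have been prompted by a suspected problem, and some of the draws from patients who stop early; Protocol 10.2 lists laboratory abnormality among the reasons for stopping.

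By-visit counts are no substitute. One patient can appear at several visits, so the counts cannot be added. Any single visit's count shows only those affected at that visit.

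The SAP is also uneven here. Section 6.1.3 lets unscheduled efficacy values enter analyses through the windows but bars unscheduled safety values. Section 6.15.6.1 plans a summary of treatment-emergent ECG abnormalities among patients with at least one post-application ECG. Laboratory data have no equivalent.

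**Working it through.** The documents state no figure on this point, so there is nothing to reproduce. The check follows each type of value through the rules and then counts days.

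**Unscheduled values.** All post-baseline unscheduled values are excluded from summaries by rule (SAP 6.1.3), whatever their grade.

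**Early-termination values: inputs**
- Windows (SAP 6.1.3): eleven, contiguous from Day 9 to Day 239.
- Weeks with a laboratory summary (SAP 6.15.5): 4, 8, 12, 16 and 24.
- Weeks without one: 2, 6, 10, 14, 20 and 32, so 11 − 5 = 6 windows.
- Days before Day 9 belong to no window.
- Early-termination timing is not given. Assumption: days are evenly spread over the range considered.

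**Days with no laboratory table**
- Weeks 2, 6, 10 and 14: 14 days each (for example 22 − 9 + 1), 4 × 14 = 56.
- Week 20: 158 − 128 + 1 = 31.
- Week 32: 239 − 198 + 1 = 42.
- Days 2 to 8: 7.

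Share affected = days with no laboratory table ÷ days in the range.

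| Range | Days with no table | Days in range | Share |
|---|---|---|---|
| 9–127 | 56 | 119 | 47.1% |
| 2–197 | 7 + 56 + 31 = 94 | 196 | 48.0% |
| 9–239 | 56 + 31 + 42 = 129 | 231 | 55.8% |
| 2–112 | 7 + 56 = 63 | 111 | 56.8% |
| 9–106 | 56 | 98 | 57.1% |
| 2–106 | 7 + 56 = 63 | 105 | 60.0% |

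By windows alone the share is 47–60%.

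**An unclear rule that could raise the share.** SAP 6.1.3 also drops a mapped value in this case: "If an assessment's mapped visit is a visit at which the subject has data from a scheduled visit present". The rule stands among the efficacy provisions, so applying it to safety data is only one possible reading. On that reading, with scheduled visits assumed to fall on their target days, an early-termination draw later than the target day is also dropped:
- Days 2–112: kept days are 7 + 7 + 7 + 6 = 27, so 84/111 = 75.7% are lost.
- Days 9–239: kept days are 4 × 7 + 11 = 39, so 192/231 = 83.1% are lost.

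**When a patient is actually missed.** A patient is missed only if Grade 3–4 is never seen at a summarized visit. A Grade 2 scheduled value that rises to Grade 3 on an unscheduled repeat is missed. A Grade 3 scheduled value that is then repeated is not, because the scheduled value is counted.

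**The case against.** The strongest reply is that clinically significant abnormalities already reach a table by arm. Protocol 9.1.4, 9.1.5.1 and 11.8 make them AEs, and SAP 6.15.4 summarizes TEAEs by treatment group, system organ class, preferred term and severity, whatever the visit type. All values are listed as well. No laboratory abnormality is an AE of special interest (Protocol 9.1.7), and leaving unscheduled draws out of by-visit tables sensibly keeps one value per patient per visit.

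Much of this stands. It narrows the gap and supports keeping the by-visit tables. It does not close the gap. AE entry depends on the investigator's judgement of significance. Protocol 9.1.4 requires a diagnosis rather than a test result, and AE severity is mild, moderate or severe rather than the laboratory grade. The AE tables therefore cannot recover Grade 3–4 incidence by parameter, and a listing gives no incidence by arm.

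A reader might infer three stronger things that the documents do not support.

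- *Most early-termination values are lost.* Early-termination data are mapped, not excluded. Whether the share exceeds half depends on the range: 57.1% for Days 9–106, but 47.1% once the Week 16 window is included. Both need the even-spread assumption.
- *Grade 3–4 abnormalities will be undercounted.* Only that they can be. The one laboratory example in Protocol 7.8 is a repeat of an abnormal value; the first value may already be counted, and the repeat may show resolution.
- *The loss can be sized from the chance that a four-weekly sample hits a short episode.* That chance describes the sampling schedule, not the exclusion rule. An episode with no extra draw is missed under any table.

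**Conclusion.** The point holds in a limited form. Grade 3–4 values seen only at an unscheduled draw, or only at an early-termination visit mapped to a week with no laboratory summary, are absent from the laboratory tables by arm. With no any-time or worst-grade table planned, the number of patients ever reaching Grade 3–4 can be undercounted. For that number the error cannot run the other way.

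The excluded share is all post-baseline unscheduled values, and roughly half of possible early-termination days (47–60% by windows alone, assuming an even spread). The higher figures of about 76% and 83% depend on a reading of the displacement rule that the SAP does not settle. These are shares of days, not of patients or events. The documents give no rates for Grade 3–4 values, unscheduled draws or dropout, so the undercount itself cannot be computed.

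This is a gap in a safety summary that is cheap to close. It does not affect any efficacy analysis.

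**What to change.** Add to SAP 6.15.5 the number and percentage of patients by worst post-baseline severity grade, for each parameter and treatment group, using all post-baseline values: scheduled, unscheduled and early termination. Keep the by-visit tables as they are. Word the exclusion in SAP 6.1.3 so that it applies to by-visit summaries only; otherwise it would contradict the new table. In the same edit, state whether the rule giving precedence to scheduled data applies to safety data.

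The cost is one extra table per laboratory panel and two sentences in SAP 6.1.3. No new data are needed, because unscheduled samples already go to the central laboratory and its results reach the clinical database.

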6.1.4 Visit Windowing for ADIQ

ADIQ is recorded by the subjects using an electronic diary with the date of entry recorded. Since ADIQ is not captured at the clinic for a specific visit the ADIQ diary data will be windowed into the appropriate study visit for analysis as outlined below.

Baseline ADIQ

The baseline ADIQ will be identified using the definition in Section 6.1.2 Baseline Definition.

Post-baseline ADIQ

First, an ADIQ recorded on the same day as a study visit will be mapped to that study visit and flagged for analysis if occurring at a scheduled study visit. If a visit ranges over multiple days the start date of the visit will be used for mapping. Note, unscheduled and early termination visits will be mapped to planned study visits using Section 6.1.3 Visit Windowing prior to this step. All remaining ADIQ will be mapped using the analysis windows presented in the following table.

Analysis Windows

Scheduled Visit	Target Study Day	Window (Days)
Week 2	15	9 to 22
Week 4	29	23 to 36
Week 6	43	37 to 50
Week 8	57	51 to 64
Week 10	71	65 to 78
Week 12	85	79 to 92
Week 14	99	93 to 106
Week 16	113	107 to 127
Week 20	141	128 to 158
Week 24	169	159 to 197
Week 32	225	198 to 239
Note: Only visits up through week 16 will be flagged for ADIQ analysis.		

If multiple ADIQ are mapped to the same analysis visit selecting an ADIQ to be flagged for analysis will follow the following steps.

- 1) If the subject had the corresponding visit, the ADIQ closest to the actual visit day will be flagged. If two ADIQ are equidistant to the actual visit day the ADIQ prior to the planned study day will be flagged.

If the subject missed the corresponding visit, the ADIQ closest to the actual planned study day will be flagged. If two ADIQ are equidistant to the planned study day the ADIQ prior to the planned study day will be flagged.

6.1.5 Adjustments for Covariates

Baseline EASI will be a covariate for the primary efficacy endpoint for EASI. Baseline sleep-loss NRS will be a covariate for the secondary efficacy endpoint for sleep-loss NRS. Baseline pruritus NRS will be a covariate for the secondary efficacy endpoint for pruritus NRS. Baseline BSA involved with AD will be a covariate for the secondary efficacy endpoint for BSA involved with AD. Baseline ADIQ score will be a covariate for the secondary efficacy endpoint for ADIQ score. No other covariates are planned to be used in the analyses for this study.

6.1.6 Handling of Dropouts or Missing Data

Missing 16 week efficacy data will be imputed and subsequently analyzed. The primary method of handling missing efficacy data will be the method of MCMC multiple imputation which does not rely on the assumption of data missing at random. Additionally, the pattern of missing observations in each treatment group will not influence the missing value estimation in the other because the imputation will be conducted independently for each treatment group. The mITT population analyses and summaries on EASI and IGA will use the MCMC multiple imputation method to impute missing values up to the Week 16 visit. Missing data for Post-Week 16 visits will not be imputed.

The multiple imputation process for imputing missing EASI and IGA data and subsequent analysis will involve 4 distinct phases with these principal tasks:

1. Calculate the number of missing 16 week values for each treatment group to be estimated by MCMC. Let n_{miss} be the maximum number of missing among the two treatment groups.
2. Create a data set of subjects, one for each treatment group, with observed values and those needing estimation by MCMC. The missing values in each data set will be filled in using the MCMC method '5 x n_{miss} ' times to generate '5 x n_{miss} ' data sets. The resulting data sets for each treatment arm will be combined into one complete data set for each imputation.
3. For each complete data set, compute the necessary derived variables. Each complete data set will be analyzed with the appropriate analysis model. See Sections 6.1.5.1.1 and 6.1.5.1.2 for details.

Analyses using the Cochran-Mantel-Haenszel (CMH) statistics will be normalized using the Wilson-Hilferty transformation [4] prior to combining them using SAS® PROC MIANALYZE.

The results from these analyses will be combined into a single inference using SAS® PROC MIANALYZE.

Per-protocol population analyses and summaries on EASI and IGA will use the last observation carried forward (LOCF) imputation method to impute missing values up to the Week 16 visit. Missing data for Post-Week 16 visits will not be imputed.

Sensitivity analyses on some of the secondary efficacy variables will use non-response imputation (NRI) to impute missing values.

6.1.6.1 MCMC Multiple Imputation

6.1.6.1.1 EASI Missing Data Imputation

A total of 4 random seeds will be needed to use PROC MCMC to impute the EASI score for the four treatment groups. Those 4 random seeds have been pre-specified by using a random number generator:

- Lebrikizumab, 125 mg Q4W: seed = 1083679005
- Lebrikizumab, 250 mg Q4W: seed = 1346533179
- Lebrikizumab, 250 mg Q2W: seed = 297484487
- Placebo Q2W: seed = 424603513

For binary responses related to EASI, the binary response variables will be calculated based on the multiply imputed datasets that have been created.

6.1.6.1.2 IGA Missing Data Imputation

A total of 4 random seeds will be needed to impute IGA for the four treatment groups. Those 4 random seeds have been pre-specified by using a random number generator:

- Lebrikizumab, 125 mg Q4W: seed = 1975600090
- Lebrikizumab, 250 mg Q4W: seed = 1260832817
- Lebrikizumab, 250 mg Q2W: seed = 2036512379
- Placebo Q2W: seed = 202520365

For binary responses related to IGA, the binary response variables will be calculated based on the multiply imputed datasets that have been created. Because the MCMC algorithm is based on the multivariate normal model, imputed values for IGA will not generally be one of the discrete values used in IGA scoring (0, 1, 2, 3, or 4). Therefore, to derive the binary IGA response variable, standard rounding rules will be applied to the imputed values. For example, if a patient has an IGA score imputed as 1.4 (and assuming a Baseline IGA score of 3), the imputed value

would be rounded down to 1, and the minimum change from Baseline of 2 would have been met. This patient would be considered a responder.

After imputing with PROC MCMC, the dichotomous success rate (clear or almost clear with at least a 2-point change from Baseline) will be computed. Each complete data set will be analyzed with a CMH and a logistic regression with a factor of treatment group. The results from these analyses will be combined using SAS® PROC MIANALYZE.

6.1.7 Non-Responder Imputation

6.1.7.1 EASI Missing Data Imputation

The sensitivity analysis for the secondary dichotomized EASI score success will use NRI to impute missing values. Specifically, any patient with a missing EASI75 value at Week 16 will be treated as a non-responder for analysis purposes.

The sensitivity analysis adjusting for patients with Rescue Medication use for the dichotomized EASI score success will use NRI to impute missing values. Specifically, any patient with Rescue Medication use (defined in Section 6.12) or discontinued treatment before the Week 16 study drug administration will be treated as a non-responder. Other missing values before Week 16 will use the LOCF method. Subjects that completed treatment, but have a missing dichotomized EASI score success will use the LOCF method.

6.1.7.2 IGA Missing Data Imputation

The sensitivity analysis for the dichotomized IGA success will use NRI to impute missing values. Specifically, any patient with a missing IGA value at Week 16 will be treated as a non-responder for analysis purposes.

The sensitivity analysis adjusting for patients with Rescue Medication use for the dichotomized IGA success will use NRI to impute missing values. Specifically, any patient with Rescue Medication use (defined in Section 6.12) or discontinued treatment before the Week 16 study drug administration will be treated as a non-responder. Other missing values before Week 16 will use the LOCF method. Subjects that completed treatment, but have a missing dichotomized IGA success will use the LOCF method.

6.2 Interim Analyses and Data Monitoring

No interim analysis or data monitoring is planned for this study.

6.3 Multicenter Studies

The study will be conducted at multiple study centers in the United States. Pooling of investigational sites will not be performed for the results for analysis.

6.4 Multiple Comparisons/Multiplicity

No adjustments for multiple comparisons or multiplicity will be made.

6.5 Use of an Efficacy Subset of Subjects

Subjects randomized to study drug who received at least one dose of study medication and completed the Week 16 evaluation without any significant protocol violations will form the Per Protocol (PP) Population. The major protocol deviations will be defined at the time of evaluability evaluation, the time between the database soft lock and hard lock before unblinding.

Excluding subjects who have major protocol deviations will decrease the variability in treatment response and will allow for a better determination of dose-response relationship of study drug.

6.6 Examination of Subgroups

Not applicable to this study.

6.7 Disposition of Subjects

The number of subjects included in each analysis population (randomized, modified intent-to-treat [mITT], safety, and PP) will be summarized by treatment group and by overall. The number of subjects completed and discontinued (including the primary reason for discontinuation) will be summarized for each treatment group and by overall. Additionally, the number of subjects that discontinued study at or prior to Week 16 will be summarized for each treatment group and by overall.

Subjects who are excluded from an analysis population will be summarized by the reasons for exclusion. Reasons subjects were not randomized will be summarized for subjects who did not enroll in the study.

6.8 Protocol Deviations

Protocol deviations will not be entered into the database. Only deviations leading to exclusion from analysis populations will be identified and summarized.

6.9 Data Sets Analyzed

Subjects will be presented/summarized based on the reason(s) for exclusion.

6.9.1 Randomized Population

All subjects who are randomized to study treatment will be included in the randomized population and will be analyzed according to the treatment group they were randomized.

Listings and summaries will be provided for all randomized subjects. Listing will also include screen failure subjects.

6.9.2 Modified Intent-to-Treat Population

All subjects in the randomized population who received least one dose of study drug will be included in the mITT population and analyzed according to the treatment group they were randomized. All efficacy analyses will be presented using the mITT population.

6.9.3 Safety Population

All subjects who were randomized and had at least one dose of study drug will be included in the safety population and analyzed according to the treatment group they received. All safety analyses will be performed using the safety population.

6.9.4 Per-Protocol Population

All subjects in the safety population who complete the Week 16 evaluation without any significant protocol violations will be included in the PP population and analyzed according to the treatment group they received. The PP population will include subjects in the safety population who do not meet any of the following criteria:

- Violated the inclusion/exclusion criteria;
- Have taken any interfering concomitant medication;
- Did not attend the Week 16 visit;
- Missed more than 1 post-baseline study visit prior to Week 16;
- Did not receive at least 75% of the expected injections of study drug during participation in the study;
- Out of visit window at the Week 16 visit by ± 3 days;

Subjects who discontinue from the study due to an AE related to study treatment will be included in the PP population. Prior to breaking the blind, other additional criteria may be added to the list to accommodate for unforeseen events that occurred during the conduct of the trial that result in noteworthy study protocol violations.

All efficacy analyses will be performed on the PP population.

